### **Description of Study Procedures (Baseline 1, Startle Study, Baseline 2 and Weeks 1-8)**

All eligible participants with a CRP>3mg/L and a Fatigue Score  $\geq 4$  will complete Baseline 1, be randomized to receive riluzole (100 mg/d) or placebo at Baseline 2, and proceed to study visits at Weeks 1, 2, 4, and 8.

During the Baseline 1 visit and on Week 1 and Week 8, subjects will undergo magnetic resonance spectroscopy (MRS). Between baseline 1 visit and baseline 2 visit, participants will have the option of undergoing a parallel Startle Test Study protocol. This protocol will consist of either 1 or 2 visits, for completing psychiatric assessments and self-report forms and for completing a psychophysiological startle task. A schedule of all assessments is provided in Table 1. Approximately 30 mL of blood will be drawn at the same time of day between 8-10AM (to reduce potential circadian effects) under sterile conditions at Baseline 1 and 2 and Weeks 1, 4 and 8. Screening/safety labs are not time dependent. Safety labs will be completed at Baseline 2, Week 4 and Week 8. At each visit, self-report forms with urine toxicology will occur as well as recording of concomitant medications and adverse events. Neurocognitive testing will be completed on Baseline 1, Baseline 2 and Week 8. Where indicated, participants will be administered the neurocognitive tests and the scanning sequence of the MRS will be completed based on scanner availability and at the discretion of the PI or PI's designee. Subject will be read MRI instructions 48hrs prior to Baseline 1, Week 1, and Week 8 visits to have the subject avoid specific foods, medications, alcohol and cigarettes starting 24hrs prior to the MRS scan. A light lunch/snack may be provided after the fasting lab work.

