**+ - for patients with a CRP>3mg/L and a Single Item Screening Scale for Fatigue Score ≥4**

**\* - for patients completing the main branch of the Riluzole Study**

**\*\* - for patients who opt for to complete the Startle Test Study**

**Key:**

**Main Riluzole Study**

\*Screening/ Safety Labs: CBC w/Diff, Metabolic Panel, hCG quantitative serum, TSH, Urinalysis w/micro at Screening and Week 8 only, Urine drug test all visits (test kit), except week 2 visit; Testing for CRP, Hepatitis B and C and HIV will be conducted on the screening visit only, unless otherwise approved by the PI. A Rapid C Reactive Protein finger prick may also be obtained by trained research staff using a rapid CRP finger prick test at the discretion of the investigator to expedite determining eligibility for research participation.

\*Psychiatric Assessments: WRAT-3, MMSE, CTQ, QID-S, Single Item Screening Scale for Fatigue

\*Research Blood: Cytokine Multiplex, TRP, KYN, mRNA analysis, methylation analysis, and gene analysis (collected under fasting conditions)

\*Self-Report Forms: IDS-SR, MFI, PROMIS-Fatigue, BAI, PSQI, Assessment of Pain level, PHQ-9, Single Item Screening Scale for Fatigue, Baycrest Memory Scale

\*Neurocognitive Tests:

Baseline 1 - EEfRT, Finger Tapping Task (FTT), The Trail Making Test (TMT), Digit Symbol Task, Reaction Time Task (CANTAB)

Baseline 2 - Rey Auditory Verbal Learning Test (RAVLT), Delayed Matching To Sample (CANTAB), Spatial Working Memory (CANTAB), Stroop Color and Word Test

Week 8- EEfRT, Finger Tapping Task (FTT), The Trail Making Test (TMT), Digit Symbol Task, Reaction Time Task (CANTAB), Rey Auditory Verbal Learning Test (RAVLT), Delayed Matching To Sample (CANTAB), Spatial Working Memory (CANTAB), Stroop Color and Word Test

[figure not shown]

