**Riluzole Flowchart:**

### **Randomization**

Subjects will be randomized to 100 mg of riluzole (50 mg po BID) or an identical appearing placebo in a 1:1 fashion with no stratification. Subjects will be instructed to take the study medication on an empty stomach (1 hour before or 2 hours after meals). The dosage of riluzole is based on several clinical trials that have previously used this medication to treat a number of psychiatric disorders ranging from depression to generalized anxiety disorder as well as ALS.[31] A randomly generated sequence of assignments to riluzole or placebo will be created and maintained by the study pharmacist. Subjects will be randomized in blocks of 4. If a subject drops out prior to receiving the first dose of medication, she will not be included in data analyses and her randomization assignment will “roll over” to the next recruited subject until 40 subjects have received at least one dose of medication or placebo.

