**Chemical Shift Imaging (CSI):** The application of a single voxel to a specific region limits evaluation of diffuse or global cortical and subcortical glutamate abnormalities that may occur in association with inflammation and have been proposed to occur in unipolar depression.[62] Simultaneous sampling from multiple voxels placed bilaterally on the basal ganglia gray matter, white matter and adjacent neocortical regions will provide a more expansive evaluation of relevant brain structures that have been implicated in the impact of inflammatory cytokines on behavior. CSI will be acquired using 2D Point Resolved Spectroscopy (PRESS)-based MRSI sequence using settings of TR=1590 ms, TE=30 ms, averages= 7, matrix=16×16, voxel size=11.3×11.3×15 mm^3, slice thickness=15mm. The raw files will be processed using LC Model package-Version 6.2-2b.[63]

Post Processing:

**Metabolite Spectral Fitting:** The LC Model is an operator-independent commercial software package that fits in vivo metabolite spectra using model resonances acquired from multiple compounds in standard phantom solutions. The water suppressed time-domain data will be analyzed between 1.0 ppm and 4.0 ppm without T1 and T2 correction. The basis set provided by the vendor of the LC Model[63] will be used and then scaled to account for receiver gain differences. While the entire 18 metabolite basis set would be entered during metabolite fitting, the analysis will only include metabolite variances (Cramer Rao Lower Bounds or CRLB) <25. Use of a high field strength (Prisma 3T) scanner and short TE (=30 msec) sequence has enabled us to calculate Glu/Cr with high reliability and very low metabolite variance (CRLB <10) during our previously published MRS studies.[24, 27]

**Water scaling and relaxometry:** The post processing pipeline has been developed to yield absolute quantitation, metabolite/water and metabolite/creatine values. LC model provides an automated water scaling settings which will be used (DOWS). All data (water signal and water suppressed data) will be phased followed by quantification of water relaxometry data. The relaxometry data will then be fitted to obtain water reference data and in the case of gray matter following segregation of the CSF and tissue water constituent. Finally, water signal will be scaled to that of the resulting value obtained in previous steps. The water scaling portion of the post processing will be done as soon as data is acquired.

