## 10. Statistical Analysis:

**Aim 1: To study the impact of 8 weeks of riluzole treatment on CNS glutamate concentrations in breast cancer patients with increased fatigue and high inflammation.**

**Hypothesis 1:** Breast cancer patients administered riluzole will exhibit greater decreases in basal ganglia and dACC glutamate compared to women treated with placebo.

Mixed-effects models for repeated measures (MMRM) will be employed to examine effects of group, time and their interaction on left and right basal ganglia glutamate or dACC controlling for baseline glutamate concentrations in separate analyses for each brain region. Relevant covariates including age, sex, race (white/non-white) and body mass index (BMI), socioeconomic status (as measured by household income), educational status, tumor stage, tumor receptor status (where appropriate), timing (adjuvant versus neoadjuvant) of chemotherapy and radiation (yes/no) will be sequentially tested in the models for goodness of fit (Akaike Information Criterion) and included as appropriate.

**Aim 2: To determine whether decreased CNS glutamate correlates with improved symptoms of fatigue and cognition dysfunction.**

**Hypothesis 2:** Decreased glutamate in the basal ganglia will be associated with decreased fatigue and improved motivation and processing speed. Decreased glutamate in the dACC will be associated with improved executive function and memory performance.

Random intercept linear mixed models will be used to assess whether change in left or right basal ganglia or dACC glutamate predict change in fatigue scores or change in neurocognitive function over time. Models will be adjusted for relevant clinical covariates (including IDS-SR, PSQI, BAI) as indicated above. Separate analyses will be run for each behavioral outcome (MFI, PROMIS) as well tests of cognition (HVLT-R, TMT PASAT COWAT RT FTT, RTT, and DSST) and motivation (DDT, EEfRT, Subjective Value Task, Effort and Delay Task, Daily Assessment/Mobile App Task, Gamble Task, and Go No-Go Variant Task.). Type I errors as a result of multiple testing will be controlled by using a step down Bonferroni procedure.[68]

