**Adequacy of Protection Against Risks**

Protection Against Risk:

Every effort will be taken to prevent injury or distress that may result from this study. Care will be taken to avoid bringing about undue psychological distress during the self-reported questionnaires. In the event that a subject becomes unduly distressed or scores  $>32$  on the IDS-SR (indicating moderate to severe depressive symptoms) or endorses a score  $>2$  on the suicide item of the IDS-SR (Question 18) or a score  $\geq 3$  on the PHQ-9 suicide item, the PI or his designee will be immediately contacted, and an appropriate clinical intervention plan will be developed. Emory has inpatient, outpatient and emergency room psychiatric services at all recruitment and evaluation sites. In addition, the PI [name] is a Board-certified psychiatrist and has extensive experience in administering standardized clinical assessments and handling psychiatric emergencies. As for blood drawing, standard sterile procedure for blood withdrawal will be used. Blood draws will be conducted by trained phlebotomists with

significant experience in the technique. In addition, the volume of blood withdrawn for this study will not exceed 40 mL over the course of the study (including screening and assessment visits). To minimize discomfort during the MRS scanning, patients will be provided with a head cushion and earplugs. Patients will also be informed about the progress of the procedure through a remote microphone. In the case of patients developing acute anxiety or panic, the scanning session will be terminated and patient provided enough support to cope with the feelings induced by the scanner. If a patient is uncomfortable with the skin cleansing during the psychophysiological task, it will be omitted. Patients will be told about the airblast prior to beginning the task. If they are uncomfortable with this or any part of the task, the task will be stopped. To reduce the likelihood of adverse reactions to riluzole, all patients will have a thorough history of allergic reactions reviewed and their first dose of riluzole will be administered under supervision of a study physician or nurse practitioner. In addition, all patients will be screened for evidence of liver disease including a screen for liver transaminases as well as hepatitis B and C and HIV. Liver transaminases will also be monitored at weeks 4 and 8, and subjects will be instructed to inform staff of any gastrointestinal symptoms.

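### Nothing visible in the plan requires a usable glutamate value from the only pre-dose scan before a woman is randomised, dosed and counted among the 40

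*Combined protocol and SAP*

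**What the plan says.** Section 6, Description of Study Procedures, states that eligible women "will complete Baseline 1, be randomized to receive riluzole (100 mg/d) or placebo at Baseline 2". The Table 1 footnote attached to Baseline 1, Baseline 2 and the later visits gives the same two entry conditions: "for patients with a CRP>3mg/L and a Single Item Screening Scale for Fatigue Score ≥4". Table 1 schedules MRS at Baseline 1, Week 1 and Week 8, so there is one scan before dosing and none at Baseline 2.

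The Randomization section keeps recruiting "until 40 subjects have received at least one dose of medication or placebo". Its only replacement rule concerns women who leave before dosing: "If a subject drops out prior to receiving the first dose of medication, she will not be included in data analyses". Participant Selection and Participants set a different target, namely 120 enrolled or recruited so that 40 have analysable data.

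Under MRI Scans, the spectral fitting rule is that "the analysis will only include metabolite variances (Cramer Rao Lower Bounds or CRLB) <25". Section 10 fits the Aim 1 repeated-measures model "controlling for baseline glutamate concentrations in separate analyses for each brain region", and Aim 2 uses change in glutamate. Section 10 gives no rule for a missing baseline value.

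**The concern.** The plan expects that some scans will not be finished or will not give a usable value. Section 12 lists claustrophobia as a risk and says: "In the case of patients developing acute anxiety or panic, the scanning session will be terminated". The Compensation paragraph pays for a scan only when it is completed, and the CRLB limit removes poor fits.

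The scan comes before a separate randomisation visit, so its result could be known before treatment is assigned. The visible text does not use it. A woman with no usable baseline spectrum could therefore be randomised, take up to 8 weeks of riluzole or placebo, fill one of the 40 places, and be absent from the analysis on which Section 11 says the study is powered. With 20 women per arm there is little information to spare.

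**Working it through.** **Conditions before randomisation.** The visible ones are CRP above 3 mg/L, fatigue of at least 4, and completing Baseline 1. None refers to the result of the scan. Baseline 1 holds the only pre-dose scan, so a missing baseline value cannot be recovered after the first dose.

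**The plan's own recruitment figure.** Participants assumes 120 recruited, about 50% meeting the CRP and fatigue criteria, and a dropout figure of about 20 with no unit.
- 120 × 0.50 = 60 eligible.
- If the dropout is 20 women: 60 − 20 = 40, which matches the stated target.
- If it is 20%: 60 × 0.80 = 48.

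Neither calculation has a stated allowance for unusable scans. The surplus in the second does not help under the Randomization section, which stops at 40 dosed.

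**Size of the loss.** The documents give no rate of unusable baselines, so f = 5%, 10% and 15% are assumptions, and each failure is taken as the loss of the whole woman. Formulas, with 40 dosed and equal arms:
- Usable number: n = 40 × (1 − f).
- The standard error of a difference between two arms of n/2 is proportional to √(4/n), so the inflation is √(40/n).
- Chance of at least one unusable baseline: 1 − (1 − f)^40.
- Number to dose so that 40 keep a baseline: 40/(1 − f), rounded up.

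| f (assumed) | Usable n | Lost | SE inflation | Chance of at least one | Dosed to keep 40 |
|---|---|---|---|---|---|
| 5% | 38 | 2 | √(40/38) = 1.026 | 0.871 | 43 |
| 10% | 36 | 4 | √(40/36) = 1.054 | 0.985 | 45 |
| 15% | 34 | 6 | √(40/34) = 1.085 | 0.998 | 48 |

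**On the power scale.** Section 11 states that 40 women give 80% power at d = 0.5. A two-sided two-sample t test with 20 per arm does not reproduce this: power at d = 0.5 is 0.338, and 80% power needs d = 0.91. That discrepancy is a separate matter, and this point does not depend on it. In the same test, power falls from 0.338 to 0.323, 0.308 and 0.293 at n = 38, 36 and 34, and the detectable d rises from 0.91 to 0.93, 0.96 and 0.99.

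**By region.** Section 10 fits a separate model for each region. A voxel that fails on one side removes the woman from that model only. She is lost to all of Aim 1 and to the glutamate analyses of Aim 2 only if no region is usable. The table is therefore an upper figure for a given per-scan failure rate.

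**The case against.** A good deal can be said in the plan's defence.

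- **Incomplete scans may already be covered.** MRS is a listed Baseline 1 procedure. On an ordinary reading, a woman whose scan was stopped has not completed Baseline 1. A reader might infer that women are randomised even if the scan never took place, and the wording does not support that. This leaves completed scans that fail the fit, and the absence of an explicit statement about stopped ones.
- **Fit failures may be few.** MRI Scans reports CRLB below 10 in the group's earlier studies, well inside the limit of 25. The 5% to 15% range has no source in the documents. This stands.
- **Tolerance is partly screened.** The pain scale is used to judge comfort in the scanner, and a high score may bar entry. This lowers the risk but is only a proxy for a usable scan.
- **The flowchart is not shown.** A check between Baseline 1 and randomisation could appear there, or in an operating procedure. If so, the text should say it too.
- **Bias.** A reader might infer that losing women after randomisation biases the comparison. Whether the baseline scan is usable is settled before allocation, so exclusion on that ground does not depend on arm, and any imbalance is due to chance.
- **Other analyses could keep her.** Imputing the baseline, or modelling it as an outcome, would retain a woman with later scans. Section 10 specifies neither, and neither helps a woman with no usable scan at any visit.

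**Conclusion.** The point holds in a limited form. The visible text sets no usability condition on the only pre-dose scan, counts places by first dose, and specifies a primary model that needs the baseline value. Under assumed failure rates of 5% to 15%, at most 2 to 6 of the 40 would be lost, with a standard error larger by about 2.6% to 8.5%. Those figures assume that each failure makes every region unusable; the true loss is probably smaller.

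The consequences are some lost precision and some women exposed to study drug without adding to either glutamate aim. They would still give safety and symptom data. The documents do not support a claim of systematic bias, nor a claim that every failed voxel costs a participant. The mismatch between 40 dosed and 40 with analysable data stands whatever the failure rate.

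**What to change.** In Description of Study Procedures and in Randomization, state that treatment is assigned at Baseline 2 only after the Baseline 1 MRS has been completed and the LCModel fit gives glutamate with CRLB below 25 in at least one basal ganglia voxel, the region on which the study is powered. Allow a repeat scan before Baseline 2. Record women who do not meet this as screen failures and draw no randomisation number for them, so that the blocks of 4 stay intact. Requiring only one side avoids turning away women who can still be analysed; a missing value on the other side then affects that side's model only.

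Reconcile the 40 dosed in Randomization with the 40 analysable in Participant Selection and Participants. If the flowchart already shows such a check, bring the text into line with it.

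The cost is modest. The fit must be run before Baseline 2, and the interval between the two visits is not stated, so the schedule has to leave room for it and for any repeat scan. MRI Scans already plans water scaling as soon as data are acquired. There will be a few more failures before randomisation, and the results will apply to women who can complete a scan.

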**Table 1. Schedule of Study Procedures and Assessments**

Procedures for MRS Controls	Intake	Screen Visit	Baseline 1 +	Startle Study (optional)	Baseline 2 + (randomization)	Week 1 +	Week 2 +	Week 4 +	Week 8 +
Informed consent	X								
Screening/ Safety labs*		X			X			X	X
Psychiatric Assessments*, **		X		X					
Medical History and Physical		X							X
Concomitant Medications		X	X	X	X	X	X	X	X
Adverse Events		X	X	X	X	X	X	X	X
MRI Safety Form		X							
Demographics		X							
Startle Task**				X					
Research Blood*			X		X	X		X	X
Urine toxicology (Test kit)		X	X		X	X		X	X
Self-Report Forms*, **			X	X	X	X	X	X	X
Neurocognitive Tests*			X		X				X
MRI Scan Food, Drink and Cigarette Intake Forms			X			X			X
MRS			X			X			X
Placebo or Riluzole (100mg/d)					X	X	X	X	X

**+ - for patients with a CRP>3mg/L and a Single Item Screening Scale for Fatigue Score ≥4**

**\* - for patients completing the main branch of the Riluzole Study**

**\*\* - for patients who opt for to complete the Startle Test Study**

**Key:**

**Main Riluzole Study**

\*Screening/ Safety Labs: CBC w/Diff, Metabolic Panel, hCG quantitative serum, TSH, Urinalysis w/micro at Screening and Week 8 only, Urine drug test all visits (test kit), except week 2 visit; Testing for CRP, Hepatitis B and C and HIV will be conducted on the screening visit only, unless otherwise approved by the PI. A Rapid C Reactive Protein finger prick may also be obtained by trained research staff using a rapid CRP finger prick test at the discretion of the investigator to expedite determining eligibility for research participation.

\*Psychiatric Assessments: WRAT-3, MMSE, CTQ, QID-S, Single Item Screening Scale for Fatigue

\*Research Blood: Cytokine Multiplex, TRP, KYN, mRNA analysis, methylation analysis, and gene analysis (collected under fasting conditions)

\*Self-Report Forms: IDS-SR, MFI, PROMIS-Fatigue, BAI, PSQI, Assessment of Pain level, PHQ-9, Single Item Screening Scale for Fatigue, Baycrest Memory Scale

\*Neurocognitive Tests:

Baseline 1 - EEfRT, Finger Tapping Task (FTT), The Trail Making Test (TMT), Digit Symbol Task, Reaction Time Task (CANTAB)

Baseline 2 - Rey Auditory Verbal Learning Test (RAVLT), Delayed Matching To Sample (CANTAB), Spatial Working Memory (CANTAB), Stroop Color and Word Test

Week 8- EEfRT, Finger Tapping Task (FTT), The Trail Making Test (TMT), Digit Symbol Task, Reaction Time Task (CANTAB), Rey Auditory Verbal Learning Test (RAVLT), Delayed Matching To Sample (CANTAB), Spatial Working Memory (CANTAB), Stroop Color and Word Test

[figure not shown]
**Startle Test Study**

\*\*Psychiatric Assessments: CAPS, MINI, MPSS

\*\*Self-Report Forms: Demographics Form, Menstrual Cycle Questionnaire, CD-RISC, BDI-II, TEI, Life Events Checklist, Post Traumatic Growth Inventory, Saliva Pre-collection Questions, Post-testing questions

\*\*Startle Task: Electromyographic activity, Acoustic startle, Electrocardiogram activity, Electrodermal activity, Response keypad, Sniffin' Sticks, Saliva Collection

**Riluzole Flowchart:**

### **Randomization**

Subjects will be randomized to 100 mg of riluzole (50 mg po BID) or an identical appearing placebo in a 1:1 fashion with no stratification. Subjects will be instructed to take the study medication on an empty stomach (1 hour before or 2 hours after meals). The dosage of riluzole is based on several clinical trials that have previously used this medication to treat a number of psychiatric disorders ranging from depression to generalized anxiety disorder as well as ALS.[31] A randomly generated sequence of assignments to riluzole or placebo will be created and maintained by the study pharmacist. Subjects will be randomized in blocks of 4. If a subject drops out prior to receiving the first dose of medication, she will not be included in data analyses and her randomization assignment will “roll over” to the next recruited subject until 40 subjects have received at least one dose of medication or placebo.

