Thus, CNS glutamate may serve as a final common pathway to CNS pathology and behavioral and cognitive disturbances in breast cancer patients after treatment. Interestingly, memantine, a drug that antagonizes glutamate signaling was found to preserve cognition in cancer patients undergoing whole brain radiotherapy, indicating that blocking glutamate may have neuroprotective effects under conditions of an increased inflammatory load. Taken together, these data suggest that glutamate may be an outstanding target for reversing the behavioral pathology associated with inflammation during breast cancer and its treatment. Demonstration that targeting glutamate to reverse fatigue and cognitive changes in patients with high inflammation and could potentially help treat the long-term toxicities of breast cancer and its treatment. The goal of the current proposal is to test the hypothesis that reduction of glutamate in breast cancer survivors with fatigue and high inflammation will be associated with decreased CNS glutamate and decreased symptoms of fatigue and cognitive function including anhedonia and psychomotor slowing. To test these hypotheses the following aims are proposed:

**Aim 1: To study the impact of 8 weeks of riluzole treatment on CNS glutamate concentrations in breast cancer patients with increased fatigue and high inflammation.**

Using a double-blind randomized controlled trial design, 40 female breast cancer patients with increased fatigue ( $\geq 4$  on a 10 point scale) and high inflammation (CRP $>3$ mg/L) will be treated for 8 weeks with either riluzole or placebo (n=20 per group). At baseline and at 1 and 8 weeks of treatment, all subjects will undergo single voxel MRS to measure CNS glutamate. Voxels will be placed in the right and left basal ganglia and the dACC. In addition, chemical shift MRS imaging will be employed to explore potential glutamate changes in other brain regions of interest.

**Hypothesis 1:** Breast cancer patients administered riluzole will exhibit greater decreases in basal ganglia and dACC glutamate compared to women treated with placebo.

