### **Data and Safety Monitoring Plan (DSMP)**

Although no high risk procedures are being conducted as part of this study, we will be following patients on an FDA approved study medication for 8 weeks. For this reason, we have elected to utilize the Data Safety Monitoring Board of the Department of Psychiatry and Behavioral Sciences as a third-party oversight committee. The DSMB is described in detail below. In addition, study clinicians will be available by pager 24 hrs/7 days a week during the period between screening and study completion. Should a subject experience a study related emergency or should active suicidal ideation develop, either [name] or [name] will be immediately notified. Drs. [name] and [name] are board certified psychiatrists with extensive experience in the treatment of psychiatric emergencies. If the assessment in question was done by a clinician other than either of them, one of them will immediately contact the subject and will evaluate the need for further medical or psychiatric treatment and will arrange medical or psychiatric follow-up if indicated. They will evaluate each case individually to make a determination regarding whether the subject can remain in the study or whether the subject should be terminated in addition to receiving a mental health referral.

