#### **Stopping rules**

Individuals who exhibit significant suicidal ideation as indicated above will be discontinued from the study. Individuals who exhibit any evidence of an allergic reaction including rash, hives or difficulty breathing and individuals who exhibit more than a two-fold elevation in liver transaminases will be discontinued from the study and followed until the allergic reaction

resolves or the transaminases return to baseline. Individuals who exhibit suicidal ideation or a serious adverse reaction to riluzole will be unblinded by the study pharmacist, and clinical management will be supervised by an unblinded study physician. Patients who have taken less than 75% of their medication may be excluded from study participation. If study removal occurs at or after the 4 week study visit, the patient will undergo exit safety laboratory testing and physical examination. Urine drug tests will be conducted at each visit (except week 2) using test kits. Individuals who test positive for drugs of abuse may be terminated at the discretion of the PI.

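### A fixed, disclosed block size of 4, with no stated firewall around the unblinded study physician, lets one unblinding raise the predictability of the other three arms in that block from 1/2 to 2/3

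*Combined protocol and SAP*

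**What the plan says.** The Randomization section (section 6) assigns women "in a 1:1 fashion with no stratification" and adds: "Subjects will be randomized in blocks of 4". Custody is with the pharmacist: "A randomly generated sequence of assignments to riluzole or placebo will be created and maintained by the study pharmacist". If a woman withdraws before her first dose, her assignment passes to the next recruit, "until 40 subjects have received at least one dose of medication or placebo". The dosed women therefore fill complete blocks.

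The trial is double-blind, with planned exceptions. Under Stopping rules (section 12), "Individuals who exhibit suicidal ideation or a serious adverse reaction to riluzole will be unblinded by the study pharmacist", and care then passes to an unblinded study physician. No section says whether that physician is kept apart from decisions about other participants.

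Other sections leave room for discretion:

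- **Entry.** The principal investigator (PI) may waive limits on age and on psychotropic or immune-active drugs (Participants), on MMSE score and reading level (Telephone Prescreen Interview), and on pain (Self-report Forms).
- **Removal.** Adherence below 75% may lead to exclusion (Compliance), and a positive drug test may lead to termination at the PI's discretion (Stopping rules). Continuation after an overt study-related adverse event is left to an unspecified decision (Adverse Event Reporting).
- **Retention after an emergency or active suicidal ideation.** The DSMP section says of two study psychiatrists: "They will evaluate each case individually to make a determination regarding whether the subject can remain in the study".

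**The concern.** Blocking protects balance at the price of some predictability. That price is small while the blind holds. Here the block size is single and printed in the investigators' own protocol, there is one list, and first doses are given under clinical supervision (Adequacy of Protection Against Risks). Someone who tracks dosing order can therefore work out where the blocks begin and end. Once one arm in a block is revealed, that person has information about the others.

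If that information reaches someone who grants entry waivers or decides on removal, those decisions could depend on the likely arm. An identical-looking placebo does not prevent this. With 20 women per arm, a few such decisions could matter.

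Two limits apply. Selection can affect only block members who have not yet been randomised; for the others the route is removal. Outcome rating is not the exposure: the spectra are fitted with software that section 6 describes as independent of the operator, and fatigue is self-reported.

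**Working it through.** The plan gives no figure for predictability, so there is none to reproduce. As a consistency check, 40/4 = 10 full blocks and 10 × 2 = 20 per arm, which matches the stated group size.

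**1. Within a known block of size b.** With b/2 women per arm and one arm revealed, P(another member is in the opposite arm) = (b/2)/(b − 1).

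- b = 4: 2/3 = 0.667
- b = 6: 3/5 = 0.600
- b = 8: 4/7 = 0.571

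**2. More than one unblinding in a block of 4.** Of the six possible arrangements:

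- Two revealed women share an arm with probability 1/3, and the other two are then certain.
- They differ with probability 2/3, and the other two are then back at 1/2.
- Three revealed women make the fourth certain.

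**3. How many women this could touch.** The unblinding rate is not in the documents. Assume each woman is unblinded independently with probability p. Over 10 blocks:

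- Expected still-blinded women guessable at 2/3 (exactly one unblinded in the block): 10 × 4p(1 − p)³ × 3.
- Expected women known with certainty: 10 × [4p²(1 − p)² + 4p³(1 − p)].
- Chance that at least one block gives certainty: 1 − [1 − 2p²(1 − p)² − 4p³(1 − p)]¹⁰.

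| p (assumed) | Expected unblinded | Guessable at 2/3 | Certain | Any block certain |
|---|---|---|---|---|
| 2.5% | 1 | 2.8 | 0.02 | 1% |
| 5% | 2 | 5.1 | 0.10 | 5% |
| 10% | 4 | 8.8 | 0.36 | 18% |
| 20% | 8 | 12.3 | 1.28 | 55% |

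**4. How many can still be selected.** On average (3 + 2 + 1 + 0)/4 = 1.5 block members come later in the list than the unblinded woman. Some will already be randomised when she is unblinded. Assuming unblinding is uniform over the 8 weeks and accrual is 1, 2 or 4 women per month (not stated in the plan), simulation leaves about 0.95, 0.63 or 0.34 still to be randomised.

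**5. Fixed 4 against undisclosed random blocks of 4, 6 and 8 (equal chance), for the next woman in the list.**

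*One arm known, averaged over positions.* Summing over a block of size b gives (b + 1)/2 expected opposite-arm successors out of b.

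- Fixed 4: 2.5/4 = 0.625, which is also (3/4)(2/3) + (1/4)(1/2).
- Random: (2.5 + 3.5 + 4.5)/(4 + 6 + 8) = 10.5/18 = 0.583.

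*One arm known, maximum over positions.*

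- Fixed 4: 0.667.
- Random, at the start of the list: (0.667 + 0.600 + 0.571)/3 = 0.61.

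*Two consecutive women known to share an arm, maximum over positions.*

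- Fixed 4: 1.00.
- Random: the chance that the first two match is 1/3, 2/5 and 3/7 for the three sizes, and the third is then opposite with probability 1, 3/4 and 2/3. The result is (0.333 + 0.300 + 0.286)/(0.333 + 0.400 + 0.429) = 0.919/1.162 = 0.79.

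A simulation of 100,000 lists agrees with these figures.

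**6. Cost in balance.** A list of random 4/6/8 blocks stopped at 40 can be at worst 22 versus 18; about 73% of simulated lists ended exactly balanced. The variance of a difference in means scales with 1/n₁ + 1/n₂: (1/22 + 1/18)/(1/20 + 1/20) = 0.1010/0.1000 = 1.01. The standard error rises by about 0.5% in the worst case.

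**The case against.** The case for leaving the plan alone has substance. The list is held by the pharmacist, the placebo is identical, and unblinding is limited to specified events. After a single unblinding, varying the block size buys only about 0.04 on average. Entry is largely settled at screening, whereas randomisation comes at Baseline 2, so a candidate's list position is uncertain when a waiver is granted. Roll-overs can blur the count further. The Stopping rules also mandate discontinuation for several events, and the remaining triggers (adherence, drug test) are objective. All of this stands and limits the size of the problem. Some discretion remains, however: those two removals are optional once triggered, and the DSMP section leaves retention after active suicidal ideation to case-by-case evaluation.

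Stronger readings are tempting but not supported:

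- A reader might infer that the unblinded physician is one of those who control eligibility and retention. The text says only that women "will be unblinded by the study pharmacist, and clinical management will be supervised by an unblinded study physician". That fits a separate role as well as a shared one. The gap is silence, not a stated overlap.
- A reader might infer that each unblinding exposes the next three women, or makes an arm certain. The women affected are the other three in the block, some already randomised, and one unblinding never gives certainty.
- A reader might add leakage through typical side effects or to participants. Table 2 lists oral hypoaesthesia and abnormal ALT at 1% each, about 0.2 women in 20 for each. No route from block inference to participants is described.

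**Conclusion.** The concern holds as a gap in allocation concealment and blinding, not as a demonstrated bias. It rests on three facts in the text: one disclosed block size, one unstratified list, and mid-trial unblinding to a study physician without stated separation from discretionary decisions. It also assumes that staff can follow dosing order.

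The change from 1/2 to 2/3 is exact. How often it would arise depends on an unblinding rate that the plan does not give: at the assumed 2.5% to 20%, between 2.8 and 12.3 still-blinded women become guessable at 2/3, and the chance of any certain block runs from 1% to 55%. The main gain from varying the blocks is that two same-arm unblindings no longer make the next arm certain. The change is worth making because it costs little.

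**What to change.** **Randomization section.** Replace the fixed block size with permuted blocks of randomly varying size (for example 4, 6 and 8), generated and held by the study pharmacist. Keep the sizes out of the protocol and any other document the study team sees. If enrolment has begun, only the unused part of the list needs regenerating. The price is that exact 20/20 balance is no longer guaranteed; the precision loss, shown above, is negligible.

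**Stopping rules (secondary clarification).** State that the physician who learns a participant's arm takes no part in entry exceptions, retention decisions or assessments for other participants. This person should not be a DSMB member, because the DSMP section relies on that committee for third-party oversight. The change is confined to who may act on the code. It leaves the unblinding triggers and the clinical management of the affected woman as written.
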